2.2.3. Exploratory Endpoints

Part A:

- Time to first transfusion after the first 5 weeks of study drug administration
- Mean change from baseline in QOL, as assessed by the change in the five level EuroQol – five dimensions questionnaire (EQ-5D-5L) scores at the treatment assessment endpoint
- Mean change from baseline in QOL, as assessed by the change in the 12-item short form survey (SF-12[®]) at the end of treatment assessment endpoint
- Incidence of solicited symptomatic anemia at EOT
- Proportion of patients with Hgb level of ≥ 12 g/dL at the treatment assessment endpoint
- Incidence of thromboembolic events after the first 5 weeks of study drug administration
- Median time to normalization of bilirubin
- Median time to normalization of LDH
- Median time to normalization of haptoglobin
- Median time to obtain Hgb level of ≥ 12 g/dL
- Proportion of patients normalizing haptoglobin at the treatment assessment endpoint
- Proportion of patients normalizing bilirubin at the treatment assessment endpoint

- Proportion of patients normalizing LDH at the treatment assessment endpoint
- Patient's Global Impression of Change (PGIC) to assess patient's perception of changes in CAD disease burden at EOT
- Patient's Global Impression of [Fatigue] Severity (PGIS) to assess the patient's perception of changes in fatigue at EOT
- Incidence of disabling circulatory symptoms at EOT
- Total healthcare resource utilization at EOT

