5.1.3. Estimands

Following [International Conference on Harmonisation \(2014\)](#) and [National Research Council \(2010\)](#), the following estimands are considered for efficacy endpoints to provide clarity of what to be estimated and its connection to the trial objectives. [Akacha, et. al. \(2017\)](#) proposed a framework for defining an estimand using three attributes:

- The population of interest;
- The variable to be used for the clinical question, which consists of measurements at a specific timepoint. It could be a composite endpoint that incorporates post-randomization events.
- The measure of intervention effect, which accounts for potential effects of post-randomization events.

A composite estimand will be used for the primary endpoint and a hypothetical estimand will be used for lab parameter defined secondary endpoints. Alternative estimands are also proposed to either assist the interpretation of primary estimand or used for exploratory endpoints.

Composite Estimand

- Population: FAS
- Variable: A composite endpoint: endpoint response criteria, and remain in the study through at least Week 23 visit (i.e., patients who discontinued the study participation prior to Week 23, including those who discontinued prior to Week 5, are considered non-responder)
- Measure of Intervention Effect: Proportion of subjects who respond according to the variable definition

Hypothetical Estimand

- Population: FAS

- Variable: Change from baseline at treatment assessment timepoint (Weeks 23, 25, and 26), where any post-baseline value after transfusion and prohibited medication (from Week 5 to Week 26) is considered missing
- Measure of Intervention Effect: Mean change from baseline, had transfusion and prohibited medications not been available

De-Facto Estimand

- Population: FAS
- Variable: Change from baseline at treatment assessment timepoint (Weeks 23, 25, and 26)
- Measure of Intervention Effect: Mean change from baseline, irrespective of transfusion or prohibited medications

Observed Estimand

- Population: a subset of FAS, subjects who remain in the study through at least the visit of interest (e.g., Week 23) and have at least 1 evaluable parameter or score at target visits.
- Variable: Change from baseline at the visit of interest, or response at the visit of interest
- Measure of Intervention Effect: Mean change from baseline or proportion of subjects who respond, irrespective of transfusion or prohibited medications

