5.2.3. Event Time Variables

Time-to-event variables will be summarized using Kaplan-Meier estimate over time, along with median time to event and probability of an event at specific time points. Partial dates will not be imputed, hence considered unknown. In general, for subjects who do not experience the event, the time-to-event will be censored at the study day of last assessment within a study period (Part A or Part B).

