7.4. Exploratory Endpoints

7.4.1. Part A Exploratory Endpoints

The analysis of exploratory endpoints (listed in [Section 2.2.3](#)) will be based on Observed Estimand ([Section 5.1.3](#)). Additionally, summary of hemolytic parameters (Hgb, bilirubin, LDH, haptoglobin, and reticulocyte) over visit is added to the SAP to examine the time trend of the improvement. Unless specified below, the endpoints will be summarized by visit for continuous and categorical variables, and for time to event variables (e.g., time to obtain Hgb level of ≥ 12 g/dL) for the entire Part A.

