7.4.1.3. Time-to-Event Endpoints

Time-to-event endpoints include:

- Time to first transfusion after the first 5 weeks of study drug administration
- Time to first transfusion (including those in the first 5 weeks of study drug administration)
- Time to first normalization of bilirubin
- Time to first normalization of LDH
- Time to first normalization of haptoglobin
- Time to first normalization of Hgb level (≥ 12 g/dL)
- Time to first achieving 2 g/dL increase in Hgb level
- Time to first achieving 2 g/dL increase or normalization of Hgb level (≥ 12 g/dL)

The endpoints will be analyzed for FAS according to [Section 5.2.3](#). For subjects who receive a transfusion after Week 5, the time to normalization of lab parameters above will be censored at the time of transfusion.

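### Censoring time to normalisation at a post-Week 5 transfusion is informative, so Kaplan-Meier overstates the probability of normalisation; it also conflicts with the estimand assigned to these endpoints

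*SAP*

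**What the plan says.** Section 7.4.1.3 of the Part A SAP lists times to first normalisation of bilirubin, LDH, haptoglobin and haemoglobin (12 g/dL or more), and two further haemoglobin-rise endpoints. It then states that, for patients transfused after Week 5, "the time to normalization of lab parameters above will be censored at the time of transfusion". Transfusions in the first five weeks do not censor.

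The estimator is set in Section 5.2.3: "Time-to-event variables will be summarized using Kaplan-Meier estimate over time, along with median time to event", together with event probabilities at chosen times. Patients without an event follow a general rule: "the time-to-event will be censored at the study day of last assessment within a study period". No competing-event analysis is planned.

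Section 2.2.3 lists these endpoints as exploratory, for example "Median time to normalization of bilirubin". Section 7.4.1 says the analysis of exploratory endpoints "will be based on Observed Estimand". Section 5.1.3 gives that estimand's measure as "Mean change from baseline or proportion of subjects who respond, irrespective of transfusion or prohibited medications". The output list in Section 12 also labels the time-to-normalisation tables as observed.

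**The concern.** Kaplan-Meier needs a censored patient to have the same future chance of the event as those still under observation. Three places in the documents say otherwise for transfused patients:

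- The transfusion criteria (Protocol Table 1; SAP Section 3.1.2) require haemoglobin below 9 g/dL with symptoms, or below 7 g/dL without.
- SAP Section 5.1.4 says missingness due to transfusion is expected to be driven by low haemoglobin and other haemolytic markers. These are the parameters being timed.
- SAP Section 7.2 counts a transfusion between Week 5 and Week 26 as failure in the primary endpoint. Section 7.4.1.3 instead removes that patient from the risk set, and the estimator credits the patient with the remaining patients' chance of normalising.

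The normalisation curve would then read too high, in one direction only. This is a single-arm trial whose Part A analysis supports a marketing application, so no control arm carries the same bias.

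**Working it through.** **The plan's own figure.** The plan states no figure for time to normalisation. Its only power figure, 90% for the primary endpoint (n = 20, true rate 66%, success at 11 of 20 or more), reproduces at 89.7% by exact binomial. The lower Clopper-Pearson limit is 31.5% at 11/20 and 27.2% at 10/20. This point does not affect it.

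**Direction.** At each event time *u*, let *d* patients of *n* at risk normalise.

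- One minus Kaplan-Meier rises by S_KM(u−) × d/n, where S_KM falls only at normalisations.
- The Aalen-Johansen cumulative incidence rises by S_all(u−) × d/n, where S_all also falls at transfusions.

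Since S_all ≤ S_KM, the Kaplan-Meier figure is never lower. It is strictly higher once anyone normalises after another patient was censored at transfusion.

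**Size, example 1 (assumed data).** Twenty patients, the planned number. Twelve normalise, at Weeks 1, 1, 3, 3, 5, 5, 7, 9, 11, 15, 19 and 23. Of the other eight, *k* are transfused at Week 8 and the rest reach Week 26 without normalising.

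- By Week 7, seven have normalised: S = 13/20 = 0.65.
- After Week 8, 13 − k remain at risk and five more normalise, so S at Week 26 = 0.65 × (8 − k)/(13 − k).
- Cumulative incidence is 12/20 = 60% for every *k*, because nobody is otherwise censored before Week 26.

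| Transfused (k) | S at Week 26 | Kaplan-Meier | Cumulative incidence | Kaplan-Meier median |
|---|---|---|---|---|
| 2 | 0.65 × 6/11 = 0.355 | 65% | 60% | 15 weeks |
| 4 | 0.65 × 4/9 = 0.289 | 71% | 60% | 15 weeks |
| 6 | 0.65 × 2/7 = 0.186 | 81% | 60% | 11 weeks |

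The cumulative incidence curve equals exactly 10/20 = 50% from Week 15 to Week 19, so its median is 15 or 19 weeks depending on convention. Only k = 6 moves the median under either convention.

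**Size, other assumed patterns (n = 20).**

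- 13 normalise, all by Week 5, and 7 are transfused later: both methods give 65% and a median of 3 weeks.
- 13 normalise over Weeks 3 to 23: cumulative incidence is 65%. Kaplan-Meier gives 71% with 2 transfused, 80% with 4, and 100% with 7 (all transfusions in Weeks 6 to 12). Taking the median as the first time the curve reaches 50%, cumulative incidence gives 17 weeks and Kaplan-Meier 17, 15 and 13.
- 8 normalise, 7 are transfused, 5 do neither: 40% with median not reached, against Kaplan-Meier 56% with a median of 23 weeks.

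**Simulation (assumed).** 1,500 trials of 20 patients per setting. 66% respond with exponential normalisation times read at scheduled visits; 34% never normalise, and 25% to 100% of these are transfused uniformly over Weeks 5 to 26.

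| Mean time to normalisation | Mean excess at Week 26 |
|---|---|
| 2 weeks | 0.2 to 1 percentage point |
| 4 weeks | 1 to 6 points |
| 8 weeks | 2 to 14 points |
| 12 weeks | 2 to 14 points |

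The typical median did not move except in the slowest setting with every failure transfused (15 against 17 weeks).

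**The case against.** **The censoring has a purpose.** Transfused blood itself raises haemoglobin, and the SAP discards post-transfusion laboratory values elsewhere to isolate the drug's effect (hypothetical estimand, Sections 5.1.3 and 5.1.4). Censoring is the time-to-event analogue. This stands as a reason not simply to count later values as normalisation. It does not rescue the estimator. The SAP's missing-at-random argument is made for MMRM and multiple imputation, which condition on observed laboratory values; an unadjusted Kaplan-Meier does not. Even for a no-transfusion target, the curve is too high if transfused patients would have normalised less often, which the transfusion criteria imply.

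**Section 5.1.4 lets exploratory endpoints depart from the Observed Estimand where specified.** True, but Section 7.4.1.3 names no other estimand, and Section 12 still labels these outputs as observed.

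**The size is unknown and may be negligible.** This stands. The documents give no normalisation times, transfusion counts or transfusion timing. The protocol (Sections 2.2.2 and 2.2.4) describes rapid correction of anaemia in Phase 1b, which would favour the small end. On the first-event reading, patients who normalise before transfusion are unaffected.

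**The consequences are limited.** Also true. There is no formal test, transfusion is failure in the primary endpoint, and time to first transfusion, transfusion counts and by-visit normalisation proportions are all reported. The proportions use observed data, however, and do not replace a cumulative curve.

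**Conclusion.** The concern holds for the probability of normalisation. Censoring at a post-Week 5 transfusion is informative for patients not yet normalised, the bias is upward, and the rule is inconsistent with the estimand the SAP assigns. In the constructed examples the excess runs from nothing to 35 points; the simulation averages run from 0.2 to 14 points. All of these rest on assumed event and transfusion times.

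A reader might infer three stronger things that the documents do not support:

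- **That reported medians will generally be too short.** In most settings examined the median does not move.
- **That results improve as more patients fail.** Example 1 holds failures fixed at eight and varies only how many are transfused. When fewer normalise, the Kaplan-Meier figure can fall: 80% with 13 normalising and 4 transfused, 56% with 8 normalising and 7 transfused.
- **That the efficacy claim is at risk.** These endpoints are exploratory and descriptive, and the primary test is unaffected.

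This is a cheap improvement worth making.

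**What to change.** In Section 7.4.1.3, estimate time to first normalisation by cumulative incidence (Aalen-Johansen), with a transfusion after Week 5 and before normalisation as a competing event. Treat prohibited CAD treatment the same way: Protocol Section 4.1 withdraws such patients as non-responders, and Section 5.2.3 would otherwise censor them at last assessment. Take the median from that curve, report it as not reached where it stays below 50%, and state the convention for a curve sitting at exactly 50%.

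Keeping these patients at risk as not normalised to the end of Part A gives the same curve only if nobody is otherwise censored earlier. Simply deleting the censoring rule is not recommended, because donor blood could then produce a haemoglobin normalisation.

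The present Kaplan-Meier analysis may stay if labelled as a hypothetical-estimand analysis. Section 7.4.1 should state which estimand applies to the time-to-event endpoints, and Section 12 should match.

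The cost is SAP wording and a standard procedure option, with no new data. The downside is that normalisation probabilities, and sometimes medians, become less favourable.

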7.4.2. Part B Exploratory Endpoints

A separate SAP will be developed for Part B of the study.

7.5. Endpoints Based on Patient-reported Outcomes

The FACIT-Fatigue, the EQ-5D-5L, the SF-12, and the PGIC will be utilized in this study. For continuous variables, the overall score and its change from baseline will be analyzed descriptively for each time point.

When applicable missing items will be handled based on the specific patient-reported outcome (PRO) instrument. Subjects missing baseline evaluations would not be included in the PRO analyses.

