6.1.2 Day 0 visit (first dose)

On Day 0, patients will undergo the following procedures before administration of the study drug:

- Inclusion/exclusion criteria for confirmation of continued eligibility
- Serum or urine pregnancy test (if applicable)
- Vaccine titers

- Body weight
- Physical examination (brief)
- Vital signs
- 12-lead ECG
- Hematology panel
- Coagulation panel
- Clinical chemistry panel
- Urinalysis
- Solicited symptomatic anemia assessment
- QOL assessments
 - FACIT-Fatigue (see [Section 10.3](#), Appendix C)
 - EQ-5D-5L (see [Section 10.4](#), Appendix D)
 - SF-12 (see [Section 10.5](#), Appendix E)
 - PGIC (see [Section 10.6](#), Appendix F)
 - PGIS (see [Section 10.8](#), Appendix H)
- ADAs against BIVV009
- PK and PD sampling
- Disease related biomarkers
- Record healthcare resource utilization data (see [Section 10.7](#), Appendix G) since previous assessment
- Record prior and concomitant medications/procedures including transfusions
- Adverse event monitoring

At 0 hour, study drug will be infused via an indwelling IV catheter over a period of 60 ±5 minutes. Patients with underlying cardiopulmonary disease may receive a 2-hour infusion with Sponsor approval. Additionally, study drug infusion may be interrupted or slowed in the event of suspicion of an allergic reaction or anaphylaxis.

After completion of the infusion, patients will undergo the following procedures:

- Vital signs at 1 hour (±5 minutes) postdose
- 12-lead ECG at 1 hour (±15 minutes) postdose
- PK and PD sampling at 1 hour (±15 minutes) postdose.

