7.4.1.2. Response Endpoints

The response endpoints include:

- Incidence of solicited symptomatic anemia at EOT
- Incidence of thromboembolic events after the first 5 weeks of study drug administration
- Proportion of subjects with Hgb level of ≥ 12 g/dL at the treatment assessment endpoint
- Proportion of subjects normalizing haptoglobin at the treatment assessment endpoint
- Proportion of subjects normalizing bilirubin at the treatment assessment endpoint
- Proportion of subjects normalizing LDH at the treatment assessment endpoint
- PGIC and change from baseline in PGIS to assess subject's perception of changes in CAD disease burden at last scheduled visit of Part A
- Incidence of disabling circulatory symptoms at last scheduled visit of Part A
- Proportion of subjects normalizing Hgb (≥ 12 g/dL) by visit
- Proportion of subjects achieving 2 g/dL increase in Hgb by visit
- Proportion of subjects normalizing bilirubin by visit
- Proportion of subjects normalizing LDH by visit
- Proportion of subjects normalizing haptoglobin by visit

The endpoints will be summarized for FAS according to [Section 5.2.2](#).

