7.5.4. Patient Global Impression of Change (PGIC)

The questionnaire (listed in [Appendix D](#)) will be summarized as an ordinal variable by visit for the FAS.

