7.5.5. Patient’s Global Impression of [Fatigue] Severity

The change from baseline in questionnaire (listed in [Appendix E](#)) will be summarized as an ordinal variable by visit for the FAS.

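### The rule dropping patients without a baseline from the PRO analyses does not exempt PGIC, which is itself a rating of change and is never differenced from baseline

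*SAP*

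**What the plan says.** **The rule.** Part A SAP, Section 7.5, opens by naming the instruments: "The FACIT-Fatigue, the EQ-5D-5L, the SF-12, and the PGIC will be utilized in this study". Its second paragraph ends: "Subjects missing baseline evaluations would not be included in the PRO analyses". No instrument or type of output is exempted. Part B SAP, Section 7.2.3, lists PGIC as a categorical PRO endpoint and carries the same sentence.

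**What PGIC is for.** Part A SAP, Section 2.2.3, makes it an exploratory endpoint: "Patient's Global Impression of Change (PGIC) to assess patient's perception of changes in CAD disease burden at EOT".

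**How PGIC is analysed.** Section 7.4.1.2 lists it with the response endpoints and separates it from the severity scale (PGIS): "PGIC and change from baseline in PGIS to assess subject's perception of changes in CAD disease burden at last scheduled visit of Part A". Section 7.5.4 says that the PGIC questionnaire "will be summarized as an ordinal variable by visit for the FAS". Section 7.5.5, on PGIS, begins instead with "The change from baseline in questionnaire".

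**When PGIC is collected.** Protocol Section 6.1.2 puts it among the Day 0 quality-of-life assessments, under the lead-in "On Day 0, patients will undergo the following procedures before administration of the study drug". Table 3 of the protocol also marks it at baseline, at three Part A visits, at Week 26, every 3 months in Part B and at the final visit.

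**The concern.** A baseline is needed when the output is a difference from baseline. PGIC asks the patient to rate change directly, so a rating at Week 26 can be used whether or not a Day 0 form exists. The exclusion is worded for all PRO analyses, so taken at its word it would delete a valid Week 26 rating for want of a value that no analysis uses. The same applies to summaries of observed values, such as the EQ-5D response categories by visit.

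Other parts of the SAP point to a different denominator. Two programmers could each defend a different PGIC table from the same data. In an open-label, single-arm trial of about 20 patients, that choice should be settled in the plan and not once the data are visible.

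**Working it through.** **1. Which outputs need a baseline?** Taken from Part A SAP Sections 5.1.4.1, 7.4.1 and 7.5.1 to 7.5.5, and the table list in Section 12.

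| Output | Uses a baseline value? | Effect of the rule on a patient without one |
|---|---|---|
| FACIT-F change (MMRM with baseline as covariate) | Yes | None beyond what the model already does |
| EQ-5D index and VAS, change | Yes | None; no difference can be formed |
| SF-12 scores, change | Yes | None; same reason |
| PGIS, change | Yes | None; same reason |
| PGIC, ordinal by visit | No | Valid ratings removed |
| EQ-5D descriptive system, by visit | No | Valid answers removed |
| PGIS and scale scores, observed values by visit | No | Valid values removed |

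For change scores the rule is redundant. Its only practical effect is on outputs that need no baseline.

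**2. What does the rest of the SAP give as the denominator?**

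- Section 5.1.3, Observed Estimand: subjects still in the study at the visit of interest with an evaluable score there. When the variable is a response, no baseline condition is listed. Sections 5.1.4 and 7.4.1 assign this estimand to the exploratory endpoints.
- Section 5.2.2, to which Section 7.4.1.2 refers for PGIC: percentages use subjects with non-missing data for that summary.
- Section 7.5.2: EQ-5D percentages use subjects assessed at the respective visit.
- Section 7.5.4: PGIC is summarised for the FAS.
- Part B SAP, Sections 5.1.3 and 5.2.2: observed data, with the same non-missing denominator.

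All of these keep a patient who has a rating at the visit. The sentence in 7.5 (Part B 7.2.3) removes that patient. Section 5.1.4, on exploratory endpoints, and Section 5.2.2 both yield where something else is specified, and the 7.5 sentence could be taken as that specification. The text therefore does not resolve the conflict.

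**3. Size.** The documents do not say how many patients lack a baseline PRO evaluation. Assume m = 0 to 3 of n = 20, all with a Week 26 PGIC rating. Share lost = m/20; denominator = 20 − m. For illustration, also assume 14 of 20 (70%) would report improvement. The reported rate then lies between (14 − m)/(20 − m), if all those dropped had improved, and 14/(20 − m), if none had.

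| m | Denominator | Ratings lost | Reported rate, range |
|---|---|---|---|
| 0 | 20 | 0% | 70% |
| 1 | 19 | 5% | 13/19 = 68.4% to 14/19 = 73.7% |
| 2 | 18 | 10% | 12/18 = 66.7% to 14/18 = 77.8% |
| 3 | 17 | 15% | 11/17 = 64.7% to 14/17 = 82.4% |

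If each patient independently lacks a baseline with probability q, the chance that at least one of 20 is affected is 1 − (1 − q)^20: 33% at q = 2%, 64% at 5% and 88% at 10%. These values of q are assumptions. The Part B FAS is the part of the Part A group dosed in Part B, so there each patient weighs 5% or slightly more.

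**4. The plan's own design figure.** With n = 20, success at 11 or more responders and a true rate of 66%, exact binomial power is 0.897 against the stated 90%. PGIC plays no part in that figure, and it does not change.

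**The case against.** The best case for the plan is that the sentence was never meant to reach PGIC. The paragraph before it deals with scores and their change from baseline, the term for the missing baseline evaluations is not defined, and Sections 7.4.1.2, 7.5.4 and 7.5.5 already treat PGIC as needing no differencing. On that view the specific text governs and nothing would be lost. This has force, and it is why the point is a clarification. It does not dispose of the point. PGIC is named in the same section as the rule, and the reference to the FAS in 7.5.4 is also used for FACIT-F, EQ-5D and SF-12, so it cannot by itself override the rule.

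A reader might infer more than the documents support:

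- *That ratings will be lost.* Loss occurs only if a patient lacks a baseline evaluation, and no count is given.
- *That the Day 0 PGIC answer is meaningless.* It is given before the first dose, so it cannot reflect treatment. The form is not reproduced, however, so its wording and reference period cannot be checked.
- *That the PGIC table will show a Day 0 column resembling a baseline.* No table shell is shown, and the Part A table list does not describe the PGIC table as by visit. Part B summaries start at Week 27, which rules it out there.
- *That the Day 0 form should be withdrawn.* Collecting it harms no stated analysis, and the Part B SAP introduction describes Part A assessments as already done.

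**Conclusion.** The point holds as a minor inconsistency in a stated rule. Both SAPs exclude patients without baseline evaluations from all PRO analyses. For PGIC and observed-value summaries, that exclusion serves no analytic purpose and conflicts with the estimand, the denominator rule and the stated population. Each affected patient costs 5% of a group of about 20; the number affected is unknown and may be zero.

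The conclusion rests on a literal reading of the sentence and on PGIC being a direct rating of change, as the endpoint definition says. PGIC is exploratory and descriptive. Part A SAP Section 7.1.1 limits formal testing to the primary hypothesis, so the primary result, its error rate and its power are unaffected.

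**What to change.** In Part A SAP Section 7.5 and Part B SAP Section 7.2.3, replace the sentence with wording to this effect:

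> Subjects without a baseline value for an instrument are excluded only from that instrument's change-from-baseline outputs (FACIT-F, EQ-5D index and VAS, SF-12, and PGIS change). PGIC and all summaries of observed values include every FAS subject with data at the visit.

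Tying the rule to the instrument concerned also settles what a missing baseline evaluation means. In Part A, add that the predose Day 0 PGIC is not used as a baseline.

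The cost is a small wording change in each SAP and one further sentence in Part A. Data collection, sample size and the protocol are unchanged. If the tables have already been produced, it is enough to state how many patients the rule removed from PGIC and, if any were removed, to rerun the affected summaries.
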